5.3.1 Outcome definition and measures

The clinical outcomes and variables of interest for this study are clinical characteristics, treatment patterns, clinical status, as assessed by the physician (and the methods used in practice to assess clinical status), MF-CTCL-related healthcare utilization, as assessed by the physician (hospitalizations and emergency room visits), AEs and SAEs (e.g., dermatitis), and patient-completed symptoms and QOL questionnaires. Due to expected variability in practice patterns, no individual method of determining response, either at follow-up or in tandem with a prior assessment, is mandated and a subjective categorical assessment of response will be included in addition to quantitative measures of response, but assessments that do occur must be captured prospectively. Additionally, it is important to capture which methods were used pre-study, even where results may not be available, so that it is clear which assessments have a prior assessment that may have been considered in the physician’s evaluation of response.

For patients who do not have any assessments, an affirmative response that the patient is still under care by the site will be requested quarterly so that the absence of reported assessments can be interpreted the same as the absence of actual assessments.

The following specific outcomes and variables of interest will be evaluated:

Clinical characteristics at enrollment and during study observation period.

Relevant medical history, including TNMB classification.

Use of prior MF-CTCL treatments.

Treatment patterns, including prescribing information, for the treatment of MF-CTCL (including dosing regimens, titration schemes, duration of time from initiation to discontinuation of therapy, and drug holidays for Valchlor).

Clinical status, as assessed by the physician (i.e., complete response, partial response,

stable disease, progressive disease, relapse).

Assessments (both whether or not the assessment was performed and the result of the assessment) used to define response, including, but not limited to:

- Composite Assessment of Index Lesion Severity.
- Modified Severity Weighted Assessment Tool.
- Physician's Global Assessment.
- Body Surface Area of disease.

Healthcare utilization related to MF-CTCL during the study period, as assessed by physician:

- Number of MF-CTCL-related hospitalizations.
- Number of MF-CTCL-related emergency room visits.

AEs and SAEs (e.g., dermatitis) whether or not related to Valchlor.

Patient-completed questionnaires:

- Visual Analogue Scale for pruritus (scale 0–10).
- Skindex-29.
- Mycosis fungoides / Sézary syndrome-type cutaneous T-cell lymphoma (MF/SS-CTCL).

5.3.2 Exposure definition and measures

Start of observation is defined as date of signed informed consent.

End of observation is defined as EOS, including death, withdrawal of consent, loss to follow-up, or study completion, whichever occurs first.

Total exposure time is defined as the date of first Valchlor exposure to the date of last Valchlor exposure.

Total on-study Valchlor exposure time is defined as the first day of Valchlor use to last day of Valchlor use during the observation period. If the patient was using Valchlor at end of observation, the last on-study day of Valchlor use is equal to the end date of observation period. Drug holidays are excluded from the sum of exposure time.

5.3.3 Covariate definition and measures

The following covariates will be considered for analyses as well as for exploring their relationship to safety-related (e.g., dermatitis) outcomes:

Age at enrollment, gender, race/ethnicity.

MF-CTCL medical history:

- Time since diagnosis and TNMB classification.

Medical history of previous and ongoing clinically significant underlying diseases and comorbid conditions.

Prior exposure to Valchlor and other MF-CTCL specific therapies.

5.4 Data sources

Data elements to be collected include the following: patient demographics, personal and family medical history, including MF-CTCL diagnosis date and etiology, current and historical MF-CTCL treatments, clinical status (as assessed by the physician), and which assessments were used to define response, MF-CTCL-related healthcare utilization (as assessed by the physician), AEs and SAEs whether or not related to Valchlor, deaths, patient-completed symptoms and QOL questionnaires. [Table 1](#) provides an overview of the variables collected at enrollment and during the observation period [see [Section 5.3.2](#) for definition]. For patients who do not have any visits, an affirmative response that the patient is still under care by the site will be requested quarterly, so that the absence of reported assessments can be interpreted the same as the absence of actual assessments.

Since this is a real-world, observational study, there are a number of sources of bias that could potentially affect any conclusions that may be drawn. The methods used to minimize these sources of bias in this study are detailed below [see [Section 5.9](#)].

Therapies specific to MF-CTCL during the course of this study are under the direction of the participating physician and not the study protocol. As this study collects data on both incident patients and prevalent patients, it is necessary to include the date of diagnosis in the data collection forms, in order to minimize potential survivor bias effect.

5.5 Study size

This study will have an approximate enrollment of 300 patients diagnosed with MF-CTCL who are being treated with Valchlor (newly initiated or continuing treatment).

A sample size of 270 evaluable patients is needed to estimate the percentage of patients with clinical status and the percentage of patients with hospitalizations, both with a margin of error of 6 percentage points. Assuming that up to 10% of patients may be non-evaluable due to incomplete follow-up, the sample size target for enrollment should be 300.

It is projected that approximately 200 evaluable patients will be re-consented under Amendment 1. The margin of error for 200 evaluable patients will be 7%.

Additionally, it is important to be able to estimate these same percentages with a margin of error of 10 percentage points or less for key subgroups representing a third or more of the patient population (e.g., patients newly initiating Valchlor). A total of 100 patients are required to achieve a margin of error of 10 percentage points per subgroup, so that a total enrollment of 300 patients is needed.

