| | 
(including length of stay and primary admission and discharge diagnoses).
 
 ○ Number of MF-CTCL-related emergency room visits. 
Clinical status, as assessed by physician (i.e., complete response, partial response, stable disease, progressive disease, relapse).
 
Assessments (whether or not the assessment was performed and the result of the assessment) used to assess response, including, but not limited to:
 
 ○ CAILS. ○ mSWAT. ○ Physician’s Global Assessment. ○ BSA of disease. 
All AEs and SAEs (e.g., dermatitis) whether or not related to Valchlor, including reports of secondary exposures since last visit (while on Valchlor only).
 
Patient-completed questionnaires:
 
 ○ VAS for pruritus (scale 0–10). ○ Skindex-29. ○ MF/SS-CTCL. 
Patients who enrolled under the original protocol and are still ongoing in the study will be contacted and informed consent will be obtained for the Amendment 1 protocol. Patients prospective data will be collected up to a total of 24 months from the original enrollment date.
 |
| STUDY SIZE | 
This study will enroll approximately 300 patients diagnosed with MF-CTCL who are being treated with Valchlor.
 
A sample size of 270 evaluable patients is needed to estimate the percentage of patients with clinical status and the rate of hospitalizations, both with a margin of error of 6 percentage points. Assuming that up to 10% of patients may be non-evaluable due to incomplete follow-up, the sample size target for enrollment should be 300. It is projected that approximately 200 evaluable patients currently enrolled will be re-consented and newly enrolled will be consented under Amendment 1 for a 2-year follow-up. The margin of error for 200 evaluable patients will be 7%.
 
Additionally, it is important to be able to estimate these same
 |

| | |
|----------------------|---|
| | 
percentages with a margin of error of 10 percentage points or less for key subgroups representing a third or more of the patient population (e.g., patients newly initiating Valchlor). A total of 100 patients are required to achieve a margin of error of 10 percentage points, so that a total enrollment of 300 patients is needed.
 |

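### The subgroup margin in Protocol 5.5 omits the plan's own 10% loss: a one-third subgroup has about 90 evaluable patients, not 100, and a worst-case margin of about 10.3 points

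*Protocol*

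**What the plan says.** Protocol section 5.5 gives two separate arguments for the study size.

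- **Overall estimate.** "A sample size of 270 evaluable patients is needed to estimate the percentage of patients with clinical status" and the percentage hospitalized, "both with a margin of error of 6 percentage points". Enrolment is then inflated for loss: "Assuming that up to 10% of patients may be non-evaluable due to incomplete follow-up, the sample size target for enrollment should be 300".
- **Subgroups.** The same percentages are to be estimated to within 10 points for important subgroups that make up at least a third of patients; those newly starting Valchlor are the example. The requirement is given as "A total of 100 patients are required to achieve a margin of error of 10 percentage points per subgroup". The section then draws its conclusion for the whole study from that figure: "so that a total enrollment of 300 patients is needed".

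Between the two, the section deals with the amendment that extends follow-up to 24 months: "It is projected that approximately 200 evaluable patients will be re-consented under Amendment 1", and "The margin of error for 200 evaluable patients will be 7" percent. The synopsis (Study size) repeats all of this. It counts newly enrolled as well as re-consented patients in the 200 and ties them to two-year follow-up. Neither place gives a confidence level, an assumed percentage, or a subgroup margin for the 200.

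**The concern.** The two arguments use different bases. The overall margin counts patients left after the 10% loss. The subgroup margin counts patients before it, since a third of 300 enrolled is exactly 100. The percentages, patients and follow-up are the same, so the same loss should apply to both.

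A reader who takes the subgroup sentence at face value will expect slightly better precision than the design gives near the one-third boundary. For two-year results the difference could be larger, because the overall margin was updated for the smaller two-year group and the subgroup margin was not.

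**Working it through.** **Inputs from Protocol 5.5 and the synopsis:** 300 enrolled; up to 10% non-evaluable; 270 evaluable for 6 points; about 200 evaluable for 7 points; 100 per subgroup for 10 points; subgroups of a third or more.

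**Assumed, because not stated:** two-sided 95% confidence and p = 0.5, the worst case.

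**Formula:** margin = 1.96 × √(p(1 − p)/n), which at p = 0.5 is 1.96 × √(0.25/n).

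**Step 1. Reproduce the plan's figures.**

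| n | Computed margin (points) | Stated |
|---|---|---|
| 270 | 5.96 | 6 |
| 200 | 6.93 | 7 |
| 100 | 9.80 | 10 |

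The inflation also reproduces: 270/0.90 = 300. At 90% confidence the three margins would be 5.0, 5.8 and 8.2, which do not match. The assumed inputs are therefore a sound reading of the plan.

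**Step 2. Apply the plan's loss to a one-third subgroup.** 300/3 = 100 enrolled; 100 × 0.90 = 90 evaluable. Margin = 1.96 × √(0.25/90) = 10.33 points. Other 95% intervals at p = 0.5 also exceed 10: Wilson 10.12, Clopper-Pearson 10.73.

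**Step 3. Evaluable patients needed for 10 points.** n = 1.96² × 0.25/0.10² = 96.04, so 97. As a share of 270 this is 97/270 = 35.9%, or about 36%, not a third.

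**Step 4. Dependence on the true percentage.** With n = 90 the margin is 10 points or less when p(1 − p) ≤ (0.10/1.96)² × 90 = 0.2343. That means p at or below about 37%, or at or above about 63%.

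**Step 5. The two-year group.** If a subgroup is also a third of the 200, it has about 67 patients. Margin = 1.96 × √(0.25/67) = 11.97 points (Wilson 11.64). Ten points would need 97/200 = 48.5%, or about 49%, of the group. With 67 patients, the margin is 10 or less only for p at or below about 22.5%, or at or above about 77.5%.

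**The case against.** The strongest reply is that the first-stage gap is trivial. The plan reports margins in whole points, and 10.33 rounds to 10. The 10% is an upper bound, enrolment is approximate, and the excess appears only for percentages near 50% in subgroups near one third. A low hospitalization percentage would meet the target even with 67 patients; the documents give no expected value. All of this stands and limits the size of the point. It does not remove the inconsistency. The plan says 100 are required, its own allowance leaves 90, and the 10 points is worded as a ceiling.

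A second reply is that the SAP (Analysis Populations) drops the separate new and continuing populations for its efficacy analyses, so the example subgroup matters less. That is partly right. However, the SAP still reports hospitalizations and emergency visits by these groups (Healthcare Resource Utilization) and still stratifies the pruritus and Skindex-29 summaries by them (Statistical Methods). The utilization results are rates over follow-up time, to which a margin for a percentage does not directly apply.

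Two stronger readings are tempting and are not supported:

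- **That 300 is unjustified.** It is not: 300 follows independently from 270 evaluable and 10% loss, and the subgroup argument is an additional one.
- **That the protocol promises 10 points for two-year subgroups and misses by 2.** It does not: for the 200 it states only the overall 7-point margin, and it gives no subgroup split. The 12.0 figure shows what the unrevised text leaves unsaid; it does not contradict a stated figure.

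**Conclusion.** The point holds as an inconsistency of modest size. The 10% allowance is applied to the overall margin and not to the subgroup margin, so a one-third subgroup has about 90 evaluable patients against a stated need of 100. That shortfall requires no assumption beyond the plan's own figures.

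Its effect on precision does rest on assumptions. At 95% confidence and p = 0.5 the margin is about 10.3 points, 0.33 above the ceiling, at the maximum planned loss. It would be wrong to infer that the subgroup target fails in general: it is met for subgroups of about 36% or more of the 270, and for percentages outside roughly 37% to 63%.

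The two-year figure of about 12.0 points is larger, but it also depends on a one-third split of the 200 that the documents do not give. It is best described as a margin the plan should state.

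**What to change.** In Protocol 5.5 and the synopsis:

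1. State that all margins are worst case, at 95% confidence and p = 0.5, and that subgroup sizes count evaluable patients.
2. Restate the subgroup precision: a one-third subgroup (90 evaluable) gives about 10.3 points, and 10 points or less holds for subgroups of at least about 36% of the 270 evaluable patients.
3. Add the two-year position: about 12 points if the subgroup is a third of 200, with 10 points needing about 49% of them.
4. Leave the total of 300 resting on the overall 6-point margin.

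The cost is wording in two places and a slightly less favourable stated subgroup figure. No extra enrolment is proposed. Holding the 10-point target for a one-third subgroup would take 97/0.90 = 107.8, so 108 enrolled per third and 324 in all. The protocol's milestones put the last first visit in Q3 2017 and the SAP is dated November 2019, so restating the margin is the practical course.

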5.6 Data management

5.6.1 Data collection

Informed consent must be obtained prior to enrollment and data collection.

Re-consent must be obtained for patients that were enrolled in the study prior to Amendment 1 and still ongoing to complete 24 months of data collection from the enrollment date. Instead of the 12 months initially planned.

This study will collect data on MF-CTCL patients being treated with Valchlor [see Section 5.2.1 for inclusion criteria] under routine clinical care. This will include both data collected from assessments that are routinely performed for MF-CTCL patients being treated with Valchlor in clinical practice, and additional data from further assessments that may be performed.

No specific clinically mandated assessments are to be performed as part of study participation. Patient-completed questionnaires, however, are a study requirement and will be collected at all clinic visits during the study observation period. These questionnaires will be administered on paper by study coordinators. Patient clinical data (non-patient-completed) will be collected from the patient's medical records at enrollment and throughout the study period. All data will be entered into an eCRF at the time of collection or on a quarterly basis by study coordinators. AEs, reports of secondary exposure, and SAEs whether or not related to Valchlor will be entered into the eCRF at every visit and upon notification by the patient (e.g., reported via phone call).

A secure, Internet-based electronic data collection (EDC) system will be used for data entry and hosting. An audit trail will be maintained by the EDC system for all data entries and changes, indicating what entries/changes have been made, who made them, and when. Data will be encrypted when transferred over the Internet and will be stored in a secure database protected from unauthorized access.

All data collected will be de-identified before transmission to the central study coordinating center. Patient names will not be collected. Other patient identifiers will be collected in order to allow identification of study patients when SAEs are received by US Drug Safety outside of the study [see Section 7.4].

All SAE data entered into the Adverse Event (AE)/Adverse Drug Reaction (ADR) Form and all reports of secondary exposure will be transferred electronically and/or by fax by the physician to Actelion US Drug Safety to be processed in the Actelion Drug Safety Database. In addition, all AE data, reports of secondary exposure, and SAE data will be entered into the study eCRF.

5.7 Data analysis

5.7.1 Analysis sets and groups

Demographics and clinical characteristics will be summarized for all enrolled patients and also grouped separately for patients continuing treatment with Valchlor versus patients who are newly initiating Valchlor. Use of prior treatments and past methods of assessing response will be similarly analyzed separately for the two groups. The methods used for assessment of response (i.e., assessed with that method versus not assessed with that method, either at follow-up alone or in tandem with a prior assessment) will be reported as cumulative percentages over time and also as a percentage of first visits, second visits, etc. To minimize the potential impact of missing data, analyses will focus on variables that are available for all patients, such as whether a particular type of assessment occurred, rather than focusing on the results of a particular assessment. Analyses of response, based on a particular measure of response, will be limited to patients for whom that measure was reported. Therefore, patients with reported data will be compared to patients without any reported data with respect to demographics and pre-treatment clinical status to identify potential biases. The summary of response rates will be tabulated and the definition of response will be detailed in the Statistical Analysis Plan.

5.7.2 Clinical characteristics

Analyses of prior treatment, assessments, and relevant medical history will be summarized for all patients enrolled and also grouped separately for patients newly initiating Valchlor versus patients continuing on Valchlor. Percentages will generally be computed as a function of non-missing data; however, if a large amount of data are missing for some historical data, a comparison of patients with missing and non-missing data may be necessary to ensure generalizability based on non-missing data alone.

5.7.3 Treatment and assessment patterns

Because relatively little prospectively collected data is available on MF-CTCL treatment patterns, preliminary analysis will make use of patient listings to develop categories of treatment patterns. Categories will be developed without cross-referencing outcomes data to minimize bias (i.e., the focus will be the presence of specific assessments, not the test value associated with the assessment). Treatments individually and in combination will be reported in percentage terms, by visit, stratified by newly initiating patients and continuing patients to identify treatment patterns.

Duration of time from first post-initiation of Valchlor office visit to discontinuation of therapy will be assessed using Kaplan-Meier estimates of freedom from discontinuation. If short-term gaps in therapy are common, sensitivity analyses may be conducted in which these gaps do or do not count as treatment discontinuations, depending on the lengths of the gaps. These analyses will focus only on newly initiated patients.

5.7.4 Clinical outcomes

The main clinical outcomes that will be analyzed are clinical response, as assessed by the physician, and MF-CTCL-related healthcare utilization, as assessed by the physician (e.g., hospitalizations and emergency room visits). Rates of on-study hospitalization and emergency room visits will be computed as the ratio of utilization counts divided by on-study days. Hospitalization-free survival will be computed using Kaplan-Meier estimates.

Because a wide variation in assessments of clinical response is expected, the clinician's subjective evaluation of response will be summarized in addition to reporting the proportion of responses among patients for whom specific tests were performed. The subjective response will be cross-classified by which assessments were used. The summary of response data is primarily a descriptive analysis to better understand how and when physicians define response, and it does not represent an estimate of the efficacy of any MF-CTCL treatment.

5.7.5 Adverse events

The frequency and percentage of patients experiencing any on-study AEs, SAEs, or death will be summarized by system organ class and preferred MedDRA terminology. Additional detail for AEs of special interest (e.g., dermatitis) will be summarized separately. SAEs will be displayed in patient listings, both including and excluding events that were not concurrent with Valchlor exposure. The definition of an on-study event is one that occurs on the day of enrollment or later, but before the date of study discontinuation or completion.

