5 RESEARCH METHODS

5.1 Study design

This is a multi-center, prospective, observational study of MF-CTCL patients who have newly initiated Valchlor or who are continuing treatment with Valchlor.

Patients will be followed by their physician according to routine clinical practice. With the exception of protocol-required patient-completed questionnaires, there are no specific or mandated clinical assessments to be performed, and patients will not receive experimental intervention or treatment as a consequence of their participation in this study. The study protocol will not mandate any specific schedule of visits. Patients will undergo clinical assessments and receive standard medical care as determined by the patient's physician in a real-world setting.

Patients will be followed prospectively for a maximum of 2 years from the date of signed informed consent until end of study (EOS), which includes withdrawal of consent, loss to follow-up, death, or study completion. Continuation in the study is not contingent on continuation of Valchlor.

The study will end after all enrolled patients have been followed for 2 years, or discontinued from the study for any reason.

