### **Exposure Definitions and Measures**

Start of observation is defined as date of enrollment.

End of observation is defined as End Of Study (EOS), which includes, adverse event, patient withdrew consent, patient lost to follow-up, physician's decision to withdraw or study completion, whichever occurs first.

Total exposure time is defined as the date of first Valchlor exposure to the date of last Valchlor exposure.

Total on-study Valchlor exposure time is defined as the first day of Valchlor use to last day of Valchlor use during the observation period. If the patient was using Valchlor at the end of observation, the last on-study day of Valchlor use is equal to the end date of observation period.

Patients may discontinue Valchlor while on study. In this case, the last day of Valchlor exposure will be when the patient discontinues Valchlor (as reported on the Valchlor treatment log). Patients who restart Valchlor after discontinuing will then begin adding Valchlor exposure days once Valchlor is restarted through the end of the study. For the patients that restart Valchlor during the study, the Total on-study Valchlor exposure will be a sum of all days in which Valchlor was dosed during the study, as reported on the Valchlor treatment log.

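### Protocol 5.7.5 ends the on-study window the day before study exit, so a death that ends observation, and any other last-day event, falls outside the on-study count

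*Protocol*

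**What the plan says.** Protocol 5.7.5 sets out the safety summary: "The frequency and percentage of patients experiencing any on-study AEs, SAEs, or death will be summarized by system organ class". It then defines an on-study event as "one that occurs on the day of enrollment or later, but before the date of study discontinuation or completion".

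Two other protocol sections fix when a patient's time in the study ends:

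- Section 5.1 follows patients "until end of study (EOS), which includes withdrawal of consent, loss to follow-up, death, or study completion", and adds: "The study will end after all enrolled patients have been followed for 2 years, or discontinued from the study for any reason".
- Section 5.3.2 states: "End of observation is defined as EOS, including death, withdrawal of consent, loss to follow-up, or study completion, whichever occurs first". For a patient still on Valchlor at that point, "the last on-study day of Valchlor use is equal to the end date of observation period".

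The SAP does not repeat the on-study definition. Its section on exposure definitions has its own list: "End of observation is defined as End Of Study (EOS), which includes, adverse event, patient withdrew consent, patient lost to follow-up". The list goes on to the physician's decision to withdraw and to study completion. Death is not in it, nor is it among the early-termination reasons in the Table 1B shell. A footnote to Tables 18 and 19 says that the overall row takes in every AE on record, including those already ongoing at enrollment. Fatal SAEs go to Listing 2.

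**The concern.** The section promises a count of on-study deaths and then defines on-study so that a death under observation cannot qualify. The death sets the end date, and the window closes before that date. The same strict limit removes any AE or SAE dated on the final day, such as a finding dated at the last visit, an event on the day of withdrawal, or a fatal event whose onset and outcome share a date.

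The rule can only lower counts. Last-day events include some of the most serious ones, and death is among the key data points that protocol 5.8 singles out for monitoring. There is also a practical risk: a programmer working from the protocol and one working from the SAP could report different totals.

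**Working it through.** The plan gives no figure on this point to reproduce. The check applies the date rule as written.

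**Inputs**

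- Event window (5.7.5): enrollment date ≤ event date < date of discontinuation or completion.
- End date (5.1, 5.3.2): the earliest of death, withdrawal of consent, loss to follow-up and completion.
- Length: 2 years, taken as day 0 to day 730, which is 731 calendar dates.

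**Step 1: is a death a study discontinuation?** The protocol does not say so in those words. Section 5.1 lists death as a study end, and leaves two ways out for a patient: the full 2 years, or discontinuation for any reason. A death before 2 years is not completion, so it falls under discontinuation.

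**Step 2: deaths.** For a death on day d, the end date is also d. The test d < d fails for every d from 0 to 730, so 0 of 731 death dates qualify. A death after an earlier withdrawal or loss to follow-up falls after observation has ended, and is not on-study under either form of the limit.

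**Step 3: other events in a 2-year completer.** The end date is day 730. The test d < 730 passes for days 0 to 729, which is 730 of 731 dates. One date is lost: 1/731 = 0.14% of dates.

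**Step 4: inclusive limit.** With event date ≤ end date, 731 of 731 dates qualify in both steps 2 and 3.

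**Step 5: a fatal SAE with earlier onset.** Take onset on day 95 and death on day 100. Since 95 < 100, the SAE is on-study under the strict rule. Only the death, dated day 100, drops out.

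**Step 6: events against exposure.** For a patient using Valchlor to day 730, 5.3.2 counts day 730 as an on-study day of use, while 5.7.5 counts events only to day 729. The two definitions have different last days.

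**Step 7: protocol against SAP**

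| Item | Protocol | SAP |
|---|---|---|
| Upper limit for AEs and SAEs | Strictly before study exit (5.7.5) | None stated (Tables 18 and 19, Listings 1 to 3) |
| Lower limit | Day of enrollment (5.7.5) | Also takes AEs ongoing at enrollment (Tables 18 and 19) |
| Death as an end of observation | Yes (5.1, 5.3.2) | Not listed (exposure definitions, Table 1B) |
| Death in the safety summary | On-study count planned (5.7.5) | Listing of fatal SAEs only |

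The SAP's tables therefore do not apply the strict limit. The SAP also supplies no other rule for the on-study death count that the protocol plans.

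**The case against.** The strongest reply is that the strict limit may never reach a reported table. SAP Tables 18 and 19 use every AE on record, and Listings 1 to 3 have no date restriction. This stands: the effect on those outputs may be nil.

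Second, 5.7.5 summarizes deaths by system organ class and preferred term, which can be read as tabulating the fatal event rather than the death itself. On that reading, a fatal SAE with onset before the last day is kept (step 5), and only same-day fatal events, or deaths coded as events in their own right, are at risk. This also stands, and it narrows the point.

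Third, the meaning of study discontinuation has to be inferred, and a programmer would see that 5.7.5 intends to report deaths. That is fair, but an evident intention that the definition contradicts is a reason to correct the definition.

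Two stronger readings are tempting and are not supported:

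- **That the study would report no deaths, and so reach a falsely favourable safety conclusion.** The protocol synopsis lists fatal SAEs, the SAE listings in 5.7.5 are not limited to on-study events, SAP Listing 2 covers SAEs resulting in death, and section 7.2 requires SAE reporting to drug safety independently of 5.7.5. Deaths can drop out of one count, not out of all reporting.
- **That the loss can be sized by projecting deaths from the median survivals in protocol section 3.** Those medians concern treated patients diagnosed at early stages. This cohort has no stage restriction and enrolls at varying times after diagnosis. Such a projection would also estimate mortality, not the number of events that the date rule removes.

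**Conclusion.** The defect is real and limited. Taken literally, 5.7.5 excludes every death that itself ends observation from the on-study death count that the same section promises, and excludes all other events dated on the last day. It also disagrees with 5.3.2 about whether the last day is on-study.

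The size is 0 of 731 admissible death dates, and one lost date out of 731 for a 2-year completer. The number of events affected cannot be derived from the documents, because it depends on how many deaths and last-day events occur and on how deaths are coded.

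The conclusion rests on two assumptions: that a death under observation counts as study discontinuation, which follows from 5.1 and 5.3.2 but is not stated outright, and that the rule is applied as written. If the analysis follows the SAP footnote instead, Tables 18 and 19 are unaffected, and what remains is an inconsistency between the two documents.

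**What to change.** 1. **Protocol 5.7.5.** Keep the start of the window and make the upper limit inclusive: *and on or before the date of study discontinuation, completion or death*.
2. **SAP, exposure definitions.** Add death to the end-of-observation list, to agree with protocol 5.1 and 5.3.2.
3. **SAP, Table 1B.** Add death to the early-termination reasons.
4. **SAP, statistical methods.** State that events dated on the end date, including death, are counted.

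The full 5.7.5 definition should not be carried into Tables 18 and 19 or Listings 1 to 3. Its lower limit would remove AEs that began before enrollment and were ongoing at that visit. The footnote to Tables 18 and 19 deliberately includes these, so counts could fall.

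The cost is a few phrases in two documents, with no new data. The one visible consequence is that reported last-day event and death counts may rise slightly.
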